After examining current literature, it is clear that vitamin D plays a crucial role in bone health and can affect the rate of skeletal-related injuries. Studies on military recruits provide promising data, but an important difference to note is musculoskeletal strength in recruits compared to conditioned athletes. Therefore, it is necessary to study the effects of vitamin D supplementation on bone health in athletes in order to help prevent stress fractures and related injuries. Our study would add to the current deficit in this area of research and would allow athletes and teams to adjust diets and training plans accordingly. The principal investigator has observed an increase rate in stress fractures in those athletes who participate in the following sports: basketball, soccer, track/field, and cross country for both male and females athletes. The overall aim is to demonstrate the evidence of stress fracture prevention in order to keep athletes performing at their highest abilities.

Objectives/Research Aims

Objectives

The main objective of this study is to find a correlation between vitamin D deficiency and stress fracture occurrences in athletes who participate in high-risk activities. These high-risk athletes undergo elevated bone turnover, which requires adequate levels of vitamin D in order to support bone health. It is hypothesized that providing supplemental treatment to athletes showing lower than normal serum vitamin D levels will decrease the occurrence of stress fractures. By recording the dates and specific occurrences of fractures, it may be possible to correlate injury rates with seasons, providing more supportive data to pre-existing literature.

This area of research is lacking in the quantity of prospective studies. Previous studies primarily focus on adolescent, elder, or military recruit populations. While literature has shown that vitamin D plays an important role in bone health, there are no previous studies that directly examine vitamin D deficiency and supplemental treatment in conditioned collegiate athlete populations. This study will add to the existing knowledge and will provide a more specific analysis for athletes.

Specific Aims

1. To compare the proportions of student athletes experiencing stress fractures during the 2015-16 academic year with the five previous years.

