2. To compare the proportions of 2015-16 academic year student athletes experiencing stress fractures in the vitamin D insufficient or deficient group and the group with vitamin D levels ≥ 30 ng/mL.
3. In 2015-16 athletes, to explore associations between the TRIAD questionnaire risk factors and low baseline vitamin D levels.
4. In 2015-16 athletes, to explore associations between the TRIAD questionnaire risk factors and subsequent stress fractures.

Setting

This study will focus on athletes who are at a higher risk of lower extremity stress fractures. Specifically, this study will be looking at male and female athletes on the track, cross-country, soccer, and basketball teams at the University of South Carolina. During the pre-season physical of each student athlete, serum vitamin D levels will be taken and recorded. There will be a certified nurse to draw the blood samples. This will take place at the University of South Carolina Athletic Department and/or the Palmetto Health Lab at [name]. Potentially, every athlete of the given teams will be enrolled in the study unless they choose not to. Only subjects showing concentrations below 30 ng/mL, which is indicative of insufficient or deficient levels, will be provided supplemental treatment of 25-(OH) vitamin D. Every enrolled subject will be monitored for injury throughout the season. Any and all injuries will be positively identified, and any confirmed stress fractures will be recorded. Data from prospective seasons will be compared to an incidence percentage of athletes from previous seasons. Previous athletes did not receive any vitamin D treatment. These will be used as a control to determine if treatment affected the occurrence of stress fractures. All physicals and tests will be performed at the USC Sports Medicine clinic by the sports medicine staff.

Resources Available

Track, cross-country, soccer, and basketball are all considered high-risk sports due to the constantly high loads being placed on the lower extremities. Basketball is also included because

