of the extreme stresses involved when jumping. Combining all four sports as a single cohort would provide an adequate number of athletes to form a test group. Each sport's season occurs at different times of the year, and indoor sports like basketball and track may have athletes with less sun exposure. This will allow a comparison of occurrences across different sports, not just between treatment and control groups. Depending on the number of individuals meeting criteria for the study, it may be necessary to extend the timeframe to multiple seasons. The initial phase of the study will include a retrospective analysis of data from deficient athletes in these sports from past seasons that have not received any supplemental treatment. This will be used to find the percentage of stress fracture incidences occurring during those seasons.

The staff directly working on the study will consist of a licensed orthopedic surgeon, a doctor of athletic training and nutrition, a physician in occupational medicine, a research assistant, and a master's student. During each individual sport's season, other athletic trainers, physicians, and coaching staff may offer assistance as well. Every individual engaged with the study will be familiar with the basics of the topic and protocol as a minimum. The physicians will provide most of the expertise and insight when providing care for the athletes. Should any unexpected consequences arise, the staff and athletes will have direct access to both orthopedic and athletic training facilities as well as the linked hospital and clinics. The staff is in constant communication and will have regular meetings in order to stay current on the progress of the study.

Prior Approvals

Each individual sports team member, along with the coaching staff, team physicians, and athletic trainers, will be informed of the study. Approval will be required from the teams listed, as well as from the University of South Carolina Orthopedic Clinic.

Study Design

a) Recruitment Methods

Potential subjects will be screened from men's and women's track and field, soccer, and basketball teams, and women's cross-country. Individual players of each described team will be informed of the study during their pre-season physical. It is hoped that every player on the specified teams will be able to enroll in the study, whether they are vitamin D deficient or not.

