Other than normal activities required for each sport, the main risk to each subject primarily involves taking blood samples. Although sampling is routine, there will still be risks of bleeding, bruising, dizziness, and possible infections. Allowing only trained individuals to take blood samples will minimize these risks. Any injury that occurs during a sports event or training activity will be handled accordingly by one of the physicians or athletic trainers on site. All injuries, regardless of nature, will be recorded per subject.

Blood samples will be tested for 25(OH) vitamin D levels using the order (Vitamin D 25-OH, Calcifediol Request). The data will be kept for each subject, day of recording, and level on an Excel spreadsheet. Any stress fracture reported will be listed on the same spreadsheet, along with the date of occurrence and severity, per subject.

Each team's athletic training staff will administer one vitamin D capsule to each team member once a week before a scheduled meeting or practice. This will help ensure every athlete takes the proper dosage, no dosages are skipped, and every week is accounted for. Athletes may still have decreased levels after the first course, and a second round of 8-week treatment will be administered. Should the second round of treatment fail to elevate vitamin D levels, the January test will confirm and treatment will continue. As many students leave to visit family during break, it will be rather difficult to monitor every athlete's levels during this timeframe.

Retrospective: The retrospective portion of the study will involve review of athletes of the same sports teams and inclusion/exclusion criteria from seasons up to four years ago. Review of previous athlete information will be drawn from electronic records kept by the athletic training staff, both electronic and hand-written records kept by the orthopedic staff, and any lab records retained at Palmetto Health. The information that will be obtained will include athlete demographics, their respective sports, stress fracture occurrences, and vitamin D levels if this was noted. The time period for the retrospective chart review will be from January 2010 through August 2015. The rate of stress fracture occurrence will be compared to the prospective treatment phase. It is important to note that individuals in the retrospective analysis will not have personal information reported, as the main purpose is to determine a baseline stress fracture rate.

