Analysis of the historic group will follow similar protocol as the recruitment of new subjects. Information from previous subjects will include including gender, age and sports team information. Additional information obtained will include stress fracture occurrence(s) and location, and vitamin D levels (if recorded).

h) Data and Specimen Banking

Data for each enrolled subject will consist of name, age, gender, ethnicity, and sports team. Any personal or private information collected will only be used during data analysis. This may contain information regarding menstruation, dietary habits, and previous pregnancies. Names and private information of subjects will not be released outside of personnel directly attached to the study, and they will not be included in the final study publication. Serum 25(OH) vitamin D levels for each subject will be recorded at the initial examination and 8 weeks following the beginning of treatment. Every injury diagnosis will be recorded per individual. There will be no blood sample banking after vitamin D levels are determined.

i) Statistical Analysis

Sample Size Justification

A power analysis was performed using PASS 2008 software on the research aim to compare the proportion of athletes that experience a stress fracture in those with normal vitamin D levels (either normal at baseline or treated by supplementation) compared to four previous years when this approach was not used. You can see that if the proportion of athletes experiencing stress fracture in the control group is 10%, then if the true reduction in the treated group was to 4% or less, we would have greater than 80% chance (power) in this study to achieve statistical significance in a test of the two proportions.

Two Independent Proportions (Null Case) Power Analysis

Numeric Results of Tests Based on the Difference: P1 - P2

H0: P1-P2=0. H1: P1-P2=D1<>0. Test Statistic: Z test with pooled variance

Power	Sample	Sample	Prop H1	Prop	Diff if H0	Diff if H1	Target Alpha
	Size Grp 1	Size Grp 2	Grp 1 or Trtmnt	Grp 2 or Control			
	N1	N2	P1	P2	D0	D1	
0.9946	200	800	0.0200	0.1000	0.0000	-0.0800	0.0500
0.9509	200	800	0.0300	0.1000	0.0000	-0.0700	0.0500
0.8220	200	800	0.0400	0.1000	0.0000	-0.0600	0.0500
0.6188	200	800	0.0500	0.1000	0.0000	-0.0500	0.0500
0.4048	200	800	0.0600	0.1000	0.0000	-0.0400	0.0500
0.2337	200	800	0.0700	0.1000	0.0000	-0.0300	0.0500
0.1224	200	800	0.0800	0.1000	0.0000	-0.0200	0.0500

Statistical Analyses

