1. To compare the proportions of student athletes experiencing stress fractures during the 2015-15 academic year with the four previous years.

A large sample test of the difference in two independent proportions will be carried out, along with computation of 95% confidence interval on the difference between the two proportions. An exploratory logistic regression model will be built with stress fracture as the outcome, group (2015-16 versus the previous four years) as the major predictor variable and type of sport and gender as covariates.

2. To compare the proportions of 2015-16 academic year student athletes experiencing stress fractures in the vitamin D insufficient or deficient group and the group with vitamin D levels ≥ 30 ng/mL.

A large sample test of the difference in two independent proportions will be carried out, along with computation of 95% confidence interval on the difference between the two proportions. An exploratory logistic regression model will be built with stress fracture as the outcome, group (baseline vitamin D deficient versus normal baseline vitamin D level) as the major predictor variable and type of sport and gender as covariates.

3. In 2015-16 athletes, to explore associations between the TRIAD questionnaire risk factors and low baseline vitamin D levels.

Exploratory descriptive and inferential statistics will be carried out, including the building of linear and logistic regression models, looking for an association between the questionnaire items and baseline vitamin D levels (continuous and dichotomized).

4. In 2015-16 athletes, to explore associations between the TRIAD questionnaire risk factors and subsequent stress fractures.

Exploratory descriptive and inferential statistics will be carried out, including the building of logistic regression models, looking for an association between the questionnaire items and the subsequent occurrence of a stress fracture.

j) Data Management

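### The Aim 1 comparison is defined inconsistently: four or five control years, deficient or all past athletes, and two descriptions of the 2015-16 group

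*Combined protocol and SAP*

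**What the plan says.** **Years.** Specific Aims, Aim 1: "To compare the proportions of student athletes experiencing stress fractures during the 2015-16 academic year with the five previous years". Statistical Analyses, item 1, compares the "academic year with the four previous years", and its logistic model also uses four. The Sample Size Justification describes a group "compared to four previous years when this approach was not used". Procedures Involved, Retrospective, reviews "athletes of the same sports teams and inclusion/exclusion criteria from seasons up to four years ago", and the same paragraph adds: "The time period for the retrospective chart review will be from January 2010 through August 2015".

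**Control population.** Resources Available describes a "retrospective analysis of data from deficient athletes in these sports from past seasons that have not received any supplemental treatment" and continues: "This will be used to find the percentage of stress fracture incidences occurring during those seasons". Setting says: "Data from prospective seasons will be compared to an incidence percentage of athletes from previous seasons". The retrospective procedures apply the same teams and eligibility criteria and do not restrict to deficient athletes. They collect a past vitamin D level only where one happens to exist.

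**2015-16 group.** Aim 1 and its analysis compare 2015-16 student athletes without restriction. The Sample Size Justification instead describes athletes whose vitamin D is normal, either at baseline or through supplementation.

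**What is not stated.** Study Timelines follows enrolled subjects from the pre-season physical to the end of their sport's activities. No per-athlete period is given for controls. Returning athletes are expected in 2015-16, but no rule says how an athlete with several seasons is counted. Section m) leaves withdrawn subjects out of the final analysis and is silent on controls.

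**The concern.** Aim 1 is the only comparison with a power calculation, and Setting names past athletes as the control for judging treatment. The control proportion is half of that result. As written, more than one control proportion could be computed, and the choice could be made after the records are seen.

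The population conflict has a direction. If deficient athletes fracture more often, a control rate taken from them alone is higher than the rate in a full roster. Setting it against all 2015-16 athletes, many of whom were never deficient, would show a reduction even if supplementation did nothing.

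**Working it through.** **1. The plan's own figure.** Inputs from the power table: N1 = 200, N2 = 800, P1 = 0.04, P2 = 0.10, two-sided alpha 0.05, pooled Z test.
- Pooled proportion: (200 × 0.04 + 800 × 0.10)/1000 = 0.088.
- Null SE: √[0.088 × 0.912 × (1/200 + 1/800)] = 0.02240.
- Alternative SE: √[0.04 × 0.96/200 + 0.10 × 0.90/800] = 0.01745.
- Power: Φ[(0.06 − 1.96 × 0.02240)/0.01745] = Φ(0.923) = 0.822. The table says 0.8220.

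**2. Four or five years.** Assume 200 athletes a year, so five years gives N2 = 1000. The pooled proportion is 0.090, the SEs are 0.02217 and 0.01679, and power is Φ(0.986) = 0.838. The difference is 0.016.

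**3. The chart-review range.** January 2010 to August 2015 covers the five academic years 2010-11 to 2014-15 plus part of 2009-10. It is wider than either definition and contains both.

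**4. Which population N2 = 800 fits.** The plan expects roughly 200 athletes, and 4 × 200 = 800. That fits all athletes counted once per season over four years. The text never says so.

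**5. Deficient-only controls against all 2015-16 athletes.** Assumptions, none fixed by the documents: no true effect; overall rate 10%; a share d of athletes deficient, with r times the risk of the others; a vitamin D level available for every past athlete. Then:
- control rate = 0.10r/(dr + 1 − d);
- N2 = 800d;
- 2015-16 group: 200 athletes at 10%.

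The false-reduction rate is the exact binomial probability that the planned test is significant in favour of 2015-16.

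| d | r | Control rate | N2 | False-reduction rate |
|---|---|---|---|---|
| 0.81 | 1.5 | 10.7% | 648 | 3.8% |
| 0.81 | 2 | 11.0% | 648 | 5.2% |
| 0.50 | 1.5 | 12.0% | 400 | 10.1% |
| 0.50 | 2 | 13.3% | 400 | 20.7% |
| 0.30 | 1.5 | 13.0% | 240 | 16.7% |
| 0.30 | 2 | 15.4% | 240 | 39.4% |

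Reference: 10% in both groups, 200 against 800, gives 2.1%. If deficient controls are compared only with deficient 2015-16 athletes (N1 = 200d, equal rates), the rate is 1.8-2.1%, so the bias disappears.

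The 81% adds the 51% insufficient and 30% deficient that the Background reports for professional football players, read as separate categories (51 + 30). If the 51% includes the 30%, about half is the relevant row. Both figures come from another population.

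**6. The 2015-16 group.** The sample size description and the Aim 1 description differ by athletes who were treated but stayed below 30 ng/mL. Procedures Involved expects some of these, because it provides for a second course. Leaving them out would select on a result obtained after baseline, which has no counterpart in the controls.

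**7. Clustering by athlete.** In a simulation with 50 entrants a year each staying four seasons, a 10% rate per season and within-athlete correlation 0 to 0.2, the mean clustered SE was 0.0230-0.0236 against 0.0237 pooled, about 3% or less. False reductions were 3.6-4.2% with the clustered SE and 1.7-2.3% with the pooled test. An unpooled test without clustering already gives 3.8% (exact, 200 against 800), so most of the rise comes from dropping the pooled variance.

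**The case against.** The case on the other side is substantial, and much of it stands.

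- The clear numerical contradiction, four against five years, is worth 0.016 of power. The chart-review dates can be read as an extraction range. Both points stand.
- The deficient-only wording is one passage under Resources Available, about an initial phase. Setting, the retrospective procedures, the analysis text and N2 = 800 all fit all athletes, and a complete deficient-only control looks infeasible when past levels exist only by chance. This makes the all-athlete reading the more likely one. It does not remove the conflict: that passage says its percentage is the past-season fracture figure, and it is not labelled as a separate analysis.
- The 39% needs both the lowest assumed deficient share and a doubled risk. That stands.

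A reader might go further and infer that control follow-up is longer than 2015-16 follow-up, or that controls are counted once as ever fractured over several seasons. Either would inflate false reductions on suitable inputs. At 5% per season, for example, ever-fractured counting over two seasons (9.75%, N2 = 400) gives 53%. The documents do not support this as a description of the plan. No passage gives unequal windows, Aim 1 is framed by academic year, and N2 = 400 departs from the plan's 800. The window, counting unit and withdrawal rule for controls are omissions to be filled, not contradictions.

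A reader might also infer that returning athletes invalidate the planned test. The simulation does not support that.

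**Conclusion.** The inconsistency is real and should be fixed. The current text gives two control periods, two control populations and two descriptions of the 2015-16 group for the only powered comparison. The stated power is arithmetically correct, and the choice of four or five years barely moves it.

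The population conflict is the consequential part. It would bias towards a false reduction only if deficient-only controls were set against all 2015-16 athletes and deficient athletes carry higher risk. The tabulated rates show direction and sensitivity under assumed shares and risk ratios. They do not estimate bias in this study, and the documents do not allow such an estimate. Nor do they show that the biased comparison is the intended one.

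**What to change.** Before chart abstraction:

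1. Use one definition in Aim 1, Resources Available, the retrospective procedures, the Sample Size Justification and the analysis text: all eligible athletes on the same teams, whatever vitamin D level is recorded, in the four academic years 2011-12 to 2014-15, against all 2015-16 athletes. Label January 2010 to August 2015 as the extraction range.
2. State that N2 = 800 counts one record per athlete-season, and apply the same sport-specific start and end dates to both groups.
3. If the deficient-only analysis is kept, label it separate and compare it only with 2015-16 athletes deficient at baseline.
4. Reconcile Procedures Involved, which keeps subjects with unrelated injuries in the study, with section m), which withdraws them. Until that is done, a common rule cannot be applied. Then use the same analysis exclusions in both groups as far as the records allow.
5. Keep the pooled Z test as primary. Report a standard error clustered by athlete and the five-year control (2010-11 to 2014-15) as sensitivity analyses.

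Cost: protocol wording and a little more abstraction work, namely a coded athlete identifier and dated control fractures. Fractures outside the common window are lost.

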Each enrolled subject will be monitored from the time of their pre-season physical to the conclusion of activities for their particular sport. The pre-season physicals will occur in August 2015, prior to the start of the school year. Subjects will be enrolled in the study even if the sports season has not begun. In the event of a study extension, any athlete partaking in a subsequent season will be asked to remain in the study as long as inclusion/exclusion criteria is met. The estimated date of completion is July of 2016, but may be extended if the data is inadequate for completion of the study.

Following the initial examination, all subjects will have serum 25(OH) vitamin D levels tested again in January. Subjects with deficient levels receiving treatment will undergo a follow-up examination 8 weeks from the initial treatment. This will help determine if subjects are responding to the treatment.

f) Study Endpoints

The primary endpoint of this study will be marked as when enough data has been collected to show a correlation between supplemental treatment and stress fracture occurrence, whether it is positive or negative. Tentatively, data collection for the study will stop at the conclusion of the last sports season. It may be necessary to extend the study for an additional school year if there are not enough data points to show a true correlation.

Supplemental treatment of 25(OH) vitamin D3 may have several adverse effects, including hypervitaminosis D and hypercalcemia. Should any subject show symptoms of these issues, they may be removed from the study.

g) Procedures Involved

Prospective: Subjects will be enrolled starting in August 2015, following the pre-season physical. It is possible many subjects, including returning athletes, may have taken summer physicals, and those subjects will be recruited and tested at a date upon return to school. Subjects should be tested prior to the start of individual seasons, although some overlap may occur. A flowchart is attached.

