Potential enrollees will be provided a simple questionnaire regarding dietary habits. This will help the researchers understand individuals' nutritional intake, more specifically vitamin D sources. They will also be provided an informative page on vitamin D function and treatment for deficiencies. During the physical, each subject will have blood drawn and baseline serum 25(OH) vitamin D3 will be recorded. Supplemental vitamin D3 treatment will be given in 50,000 IU dosages once a week for 8 weeks following the initial examination. The prescription will be: Vitamin D3 50,000 IU oral capsule take 1 pill per week for 8 weeks. Subjects receiving supplemental treatment will then have vitamin D3 levels checked again at 8 weeks to ensure serum levels have risen. These values will be recorded. Should serum levels of vitamin D3 remain below the target value of 30 ng/mL, these subjects will be treated again following the same protocol as the primary treatment to ensure the levels rise. The subjects will then be followed throughout the course of the season, including all training activities, practices, and games.

Both deficient and normal subjects will be re-tested in January upon return from winter break. Subjects showing serum 25(OH) vitamin D3 levels below normal will be given supplemental treatment of 50,000 IU dosages once a week for 8 weeks. These subjects may have new or recurring deficiencies. Serum levels will be checked again following the end of treatment to ensure levels have risen. Any subject that was within normal ranges in the fall sports season that drops to deficient ranges will be treated with the same dosage as the primary treatment. Should their serum vitamin D3 levels fail to rise after 8 weeks, a secondary treatment will be administered following the same protocol as the primary treatment.

Throughout the seasons, any subject complaining of pain or injury to the lower extremity will undergo examination by the physician in order to positively diagnosis the injury. Each positively identified stress fracture will be recorded for that subject, and the appropriate treatment and rehabilitation will ensue. The lower extremity will be defined as any portion of the femur, tibia, fibula, and bones of the foot and ankle. Should an injury occur that does not

directly relate to a stress fracture or the lower extremity, the subject will remain in the study. However, these subjects will be included in a separate analysis.

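### Follow-up ends with each athlete's own sport while Aim 1 is an academic-year proportion, and the historical at-risk window is not fixed, so the two groups may be counted over different windows

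*Combined protocol and SAP*

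**What the plan says.** Section e (Study Timelines) sets the individual window: "Each enrolled subject will be monitored from the time of their pre-season physical to the conclusion of activities for their particular sport". Two other places tie follow-up to the season. Setting says "Every enrolled subject will be monitored for injury throughout the season", and section g (Procedures Involved) says "The subjects will then be followed throughout the course of the season, including all training activities, practices, and games". Resources Available adds that "Each sport's season occurs at different times of the year".

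Aim 1 is stated over a different period: "To compare the proportions of student athletes experiencing stress fractures during the 2015-16 academic year with the five previous years". Section i repeats the academic-year comparison (with four previous years, a separate discrepancy) and tests it as a difference of two independent proportions, with no exposure time. At study level, section f says: "Tentatively, data collection for the study will stop at the conclusion of the last sports season".

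The historical window is described in two ways. Setting, Resources Available and part of section g speak of previous seasons. Section g also gives a calendar chart review from January 2010 through August 2015.

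On the mid-year test, section e says "all subjects will have serum 25(OH) vitamin D levels tested again in January", and section g says "Both deficient and normal subjects will be re-tested in January upon return from winter break". Section g provides 8 weeks of supplementation for low January values, including in athletes who had been normal in the fall. No section says how fractures are ascertained once an athlete's sport has ended.

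**The concern.** All athletes enter from August 2015, but each leaves observation when their own sport finishes. The length of observation therefore depends on the sport, and for some athletes it may be well short of an academic year. A simple proportion treats an athlete watched for a few months and fracture-free the same as one watched all year.

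The main risk lies in the Aim 1 comparison. If a historical athlete's fracture counts whenever it appears in the charts, while a 2015-16 athlete's counts only until the sport ends, the 2015-16 proportion is lower for a reason unrelated to vitamin D. The error favors the study hypothesis.

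A second consequence concerns January. The background section presents winter as the time of lower vitamin D, and the protocol re-tests and treats at that point. If an athlete's sport is already over, the protocol does not say whether a later fracture is recorded as an outcome.

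**Working it through.** **1. The plan's own figure.** Section i gives power 0.8220 for 4% versus 10%, with 200 and 800 athletes, a two-sided alpha of 0.05 and a pooled Z test.

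- Pooled proportion: (200 × 0.04 + 800 × 0.10) / 1000 = 0.088.
- Null SE: √[0.088 × 0.912 × (1/200 + 1/800)] = 0.02240.
- Alternative SE: √[0.04 × 0.96/200 + 0.10 × 0.90/800] = 0.01745.
- Power: Φ[(0.06 − 1.96 × 0.02240) / 0.01745] = Φ(0.92) = 0.822.

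The figure reproduces, and the power table contains no arithmetic error that bears on this point. The 10% and 4% are not tied to any length of follow-up.

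**2. Inputs the documents do not give.** There are no rosters by sport, no season dates, and no split of fractures between in-season and off-season. The following are assumptions:

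- a true rate of 10% per year with no treatment effect;
- a share *s* of the 200 athletes whose sport ends early, 30% to 50%;
- a fraction *w* of those athletes' fractures that falls inside the shorter window. Even hazard and 4 of 11 months (August to July) give *w* = 4/11; a milder case takes *w* = 0.7.

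Recorded rate = 10% × (1 − *s* + *s* × *w*). For *s* = 0.4 and *w* = 4/11 this is 10% × (0.6 + 0.1455) = 7.45%.

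**3. Three readings of the windows.** Probabilities come from exact binomial enumeration of the pooled Z test, 200 versus 800, counting each direction separately.

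| *s* | *w* | Short-window rate | A: only 2015-16 short, false reduction | B: both short, false reduction | C: only historical short, false increase |
|---|---|---|---|---|---|
| 0.4 | 0.7 | 8.80% | 0.063 | 0.021 | 0.086 |
| 0.3 | 4/11 | 8.09% | 0.111 | 0.020 | 0.151 |
| 0.4 | 4/11 | 7.45% | 0.176 | 0.020 | 0.234 |
| 0.5 | 4/11 | 6.82% | 0.266 | 0.020 | 0.341 |

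With full, equal windows at 10%, the false-reduction probability is 0.021. The exact value is a little below the nominal 0.025.

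**4. Sensitivity to the assumptions.** A second set (10-month year, constant hazard, 20% to 50% of athletes followed for 4 to 5 months) gives a 2015-16 rate of 7.1% to 9.0% and a false-reduction probability of 5.2% to 22.9% under reading A.

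**5. What reading B costs.** If both groups are season-limited, the bias goes but fewer events are counted. Under the assumptions in step 4, and taking 4% and 10% as full-year rates, power falls from 0.82 to about 0.64 to 0.77.

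**The case against.** The strongest reply is that activities need not mean competition. Section g's follow-up includes training and practices, and capsules are given before a scheduled team meeting or practice, so an athlete treated in January would appear still to be in team activity. All subjects are re-tested in January, so they are still in the study then. This stands as far as it goes. A reader might infer that fall-sport athletes treated in January have no outcome follow-up at all. The documents do not support that: they give no season dates, do not say which sports end in the fall, and do not limit activities to games. What they leave is follow-up that is undefined after the sport ends.

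The second reply is that the control is largely described by season, and the historical review is said to follow a similar protocol. The January 2010 to August 2015 period may be only the span of charts searched. This also stands. A reader might infer that Aim 1 is certainly biased toward benefit, but that needs a full-year comparator, which the text neither states nor excludes. Reading B shows no such bias.

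For Aim 2, both groups come from the same teams, so unequal windows matter only if low vitamin D differs by sport, and the exploratory logistic model includes sport. That model cannot repair a window difference between the prospective and historical groups in Aim 1. Nor does any aim evaluate the January treatment separately, so the January gap weakens the fracture record but defeats no stated analysis.

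The replies do not reconcile a sport-specific end with an academic-year proportion. Even if activities includes off-season training, teams may stop on different dates.

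**Conclusion.** The point holds as an unresolved conflict over the at-risk window. The individual window is sport-specific, Aim 1 is an academic-year proportion without person-time, and the historical window can be read as seasons or as calendar time. Two people abstracting the same record could reach different counts.

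The size is conditional. If activities means the competitive season and historical fractures are counted over full years, the illustrations give a false-reduction probability of about 6% to 27%, against 2.1% with equal windows. These rest on assumed sport shares, window lengths and fracture timing, and are not estimates for this study. If both groups are season-limited, the inflation disappears, but the result does not answer Aim 1 as written and has less power. Outcome follow-up after January is undefined, and may be absent, for athletes whose sport has ended. The change is worth making because it is cheap and protects the Aim 1 comparison.

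**What to change.** In sections e and g, replace the sport-specific end with one common end date for every enrolled athlete: either the end of the 2015-16 academic year or the July 2016 completion date already stated. Record every lower-extremity stress fracture up to that date, flagged as in-season or off-season.

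Apply the same August-to-end-date window to each historical year, and say so in the retrospective part of section g and in section i. Use this window for the proportions in Aims 1 and 2. Both groups must change together: reading C shows that lengthening only 2015-16 against season-limited historical counts would give a false increase with probability of about 15% to 34% under even hazard.

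The cost is small. Fracture dates are already recorded, the athletes are already re-tested in January, and the existing chart review spans complete August-to-July years from 2010-11 through 2014-15. The price is a few more months of record checks, and some athletes will leave campus before the common date.
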